# APPENDIX 5. TOPICAL STEROID POTENCY CHART

The following potency chart categorizes brand- name topical steroid medications along with the name of the corresponding generic drug. The medications are listed in order of their potency. Please note that the percentage of ingredient in the medication does not necessarily correlate with the strength of the steroid. The list may not be comprehensive.

Brand Name	Generic Name					
Class 1 – Superpotent						
Clobex Lotion/Spray/Shampoo, 0.05%	Clobetasol propionate					
Cormax Cream/Solution, 0.05%	Clobetasol propionate					
Diprolene Ointment, 0.05%	Augmented betamethasone					
Olux E Foam, 0.05%	Clobetasol propionate					
Olux Foam, 0.05%	Clobetasol propionate					
Temovate Cream/Ointment/Solution, 0.05%	Clobetasol propionate					
Ultravate Cream/Ointment, 0.05%	Halobetasol propionate					
Vanos Cream, 0.1%	Fluocinonide					
Cordran Tape, 0.05%	Flurandrenolide					
Class 2 - Potent						
Diprolene Cream AF, 0.05%	Augmented betamethasone					
Elocon Ointment, 0.1%	Mometasone furoate					
Florone Ointment, 0.05%	Diflorasone diacetate					
Halog Ointment/Cream, 0.1%	Halcinonide					
Lidex Cream/Gel/Ointment, 0.05%	Fluocinonide					
Psorcon E Cream, 0.05%	Diflorasone diacetate					
Topicort Cream/Ointment, 0.25%	Desoximetasone					
Topicort Gel, 0.05%	Desoximetasone					
Class 3 – Upper Mid-Strength						
Cutivate Ointment, 0.005%	Fluticasone propionate					
Lidex-E Cream, 0.05%	Fluocinonide					
Luxiq Foam, 0.12%	Betamethasone valerate					
Topicort LP Cream, 0.05%	Desoximetasone					
Class 4 – Mid-Strength						
Cordran Ointment, 0.05%	Flurandrenolide					

Brand Name	Generic Name				
Elocon Cream/Lotion, 0.1%	Mometasone furoate				
Kenalog Cream/Spray, 0.1%	Triamcinolone acetonide				
Synalar Ointment, 0.025%	Fluocinolone acetonide				
Westcort Ointment, 0.2%	Hydrocortisone Valerate				
Class 5 - Lower Mid-Strength					
Capex Shampoo, 0.01%	Fluocinolone acetonide				
Cordran Cream/Lotion, 0.05%	Flurandrenolide				
Cutivate Cream/Lotion, 0.05%	Fluticasone propionate				
Dermatop Cream, 0.1%	Prednicarbate				
DesOwen Lotion, 0.05%	Desonide				
Locoid Cream/Lotion/Ointment/	Hydrocortisone butyrate				
Solution, 0.1%					
Pandel Cream, 0.1%	Hydrocortisone probutate				
Synalar Cream, 0.025/	Fluocinolone acetonide				
Westcort Cream, 0.2%	Hydrocortisone valerate				
Class 6 – Mild					
Aclovate Cream/Ointment, 0.05%	Alclometasone dipropionate				
Derma-Smoothe/FS Oil, 0.01%	Fluocinolone acetonide				
Desonate Gel, 0.05%	Desonide				
Synalar Solution, 0.01%	Fluocinolone acetonide				
Verdeso Foam, 0.05%	Desonide				
Class 7 - Least Potent					
Cetacort Lotion, 0.5%/1%	Hydrocortisone				
Cortaid Cream/Spray/Ointment, 1%	Hydrocortisone				
Hytone Cream/Lotion, 1%/2.5%	Hydrocortisone				
Micort-HC Cream, 2%/2.5%	Hydrocortisone				
Nutracort Lotion, 1%/2.5%	Hydrocortisone				
Synacort Cream, 1%/2.5%	Hydrocortisone				

Abstracted from: National Psoriasis Foundation. Topical treatments for Psoriasis. 2013. http://www.psoriasis.org/document.doc?id=164 (accessed 24 February 2014).

## **DOCUMENT HISTORY**

Version	Author	Description
1.0	[name]	23-Jun-2020 New Document

#### LIST OF ABBREVIATIONS

Abbreviation	Full Term
ADI	Actual dose intensity
AE	Adverse event
ALP	Alkaline phosphatase
ALT	Alanine transaminase
ATC	American Therapeutic Chemical (Classification)
BID	Twice daily
C1D1	Cycle 1 Day 1
CI	Confidence interval
СМ	Concomitant medication
CNI	Calcineurin inhibitor
CR	Complete response
CRF	Case report form
CSR	Clinical study report
CTCAE	Common Terminology Criteria for Adverse Events
DOR	Duration of response
ECG	Electrocardiogram
EOT	End of treatment
ICH	International Conference on Harmonisation
LR	Lack of response
MedDRA	Medical Dictionary for Regulatory Activities
mITT	Modified Intent-to-treat
KPS	Karnofsky Performance Scale
NE	Not evaluable
ORR	Overall response rate
OS	Overall survival
OS-9	Overall survival at 9 months
PD	Pharmacodynamics
PDI	Planned dose intensity
PFS	progression-free survival
PFS-6	progression-free survival at 6 months
РК	Pharmacokinetics
PR	Partial response
PT	Preferred Term
RANO	Response Assessment in Neuro-Oncology criteria
RDI	Relative dose intensity
RV	Residual volume
QD	Once daily
ORR	Overall response rate
QTcF	Corrected QT interval using Fridericia's formula
SAE	Serious adverse event

Abbreviation	Full Term
SAP	Statistical Analysis Plan
SOC	System Organ Class
STB	Stable
TEAE	Treatment-emergent adverse event

# **1 INTRODUCTION**

Gliomas account for 80% of primary malignancies of the central nervous system (CNS). Glioblastomas (World Health Organization (WHO) Grade IV astrocytic tumors) account for 60–70% of gliomas and remain the most aggressive subtype. Glioblastoma occurs mostly in adults (median age of 64 years at diagnosis) with an estimated incidence of 2–3 cases per 100,000 people in Europe and North America. With 1- and 5-year overall survival (OS) rates of 29% and 3%, respectively, the prognosis of glioblastoma remains poor [Central Brain Tumor Registry of the United States 2011] and there is a need to develop more effective therapeutic approaches.

Tesevatinib (formerly known as KD019) is an orally-administered tyrosine kinase inhibitor that has been documented to inhibit multiple molecular drivers of tumor growth, including epidermal growth factor receptor (EGFR), human epidermal growth factor receptor 2 (HER2), Src, and vascular endothelial growth factor receptor 2 (VEGFR2).

This Statistical Analysis Plan (SAP) describes detailed statistical procedures to be used for study KD019-208 as specified in the protocol (Amendment No. 4, 03-Apr-2019): A Phase 2, Multicenter Study of tesevatinib Monotherapy in Patients with Recurrent Glioblastoma.

The SAP was written in accordance with the recommendations outlined in the International Conference on Harmonisation (ICH) E9 Guideline entitled "Guidance for Industry: Statistical Principles for Clinical Trials" and the most recent ICH-E3 Guideline, entitled "Guidance for Industry: Structure and Content of Clinical Study Reports."

## 2 STUDY SUMMARY

## 2.1 Study Objectives

## 2.1.1 Primary Objectives

• To evaluate the efficacy of tesevatinib as measured by investigator-assessed progression-free survival rate at 6 months (PFS-6) in mITT population.

### 2.1.2 Primary Safety Objective

• To evaluate the safety and tolerability of tesevatinib in all treated subjects.

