### 6.1.2. Primary safety objective

• To evaluate the safety and tolerability of tesevatinib in all patients and in the subgroup of patients with EGFRvIIIpos and the subgroup of patients with EGFR amplificationpos tumors

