# 6.3. Exploratory objectives

- To evaluate the plasma concentrations of tesevatinib in patients with and without systemic steroid treatment
- To evaluate the potential association of exploratory tissue and blood biomarkers with response to tesevatinib and with adverse events. These include EGFRvIII mutation and gene amplification and may include circulating tumor DNA
- To evaluate the correlation between patients with EGFRvIIIpos tumor and those patients with EGFR gene amplification
- To evaluate and compare EGFRvIIIpos expression and/or other tissue biomarkers potentially associated with response with tesevatinib, in paired primary and recurrent glioblastoma specimens from the same patient, when these are available

- To evaluate patient-reported outcomes of disease and treatment-related symptom severity and interference as measured by the MDASI-BT questionnaire
- To evaluate patient-reported outcomes of disease and treatment-related symptom severity and interference as measured by the MDASI-BT in the subgroup of patients with EGFRvIIIneg and EGFR gene amplificationneg tumors as compared to those in patients with EGFRvIIIpos and EGFR gene amplificationpos tumors

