## 13.4.6.5. Safety Data

Safety analyses will be performed on all patients who received any quantity of study drug. AEs that are not related to treatment and that occur more than 30 days after the administration of the last dose of treatment will not be reported or analyzed.

Safety analyses will present overall results and results by subgroups.

Safety observations and measurements include AEs, safety laboratory tests, vital sign measurements, physical examinations, ECG assessments, and plasma levels.

Treatment-emergent AEs will be summarized using MedDRA® (Version 18.1 or higher) System Organ Class (SOC) and preferred term, classified from verbatim terms. The incidence and percentage of patients with at least 1 occurrence of a preferred term will be included, according to the most severe grade using the NCI-CTCAE; Version 4.03. The number of events per

preferred term will also be summarized. Causality (relationship to study treatment) will be summarized separately.

AEs, SAEs, related AEs, related SAEs,  $\geq$  Grade 3 AEs, related  $\geq$  Grade 3 AEs, and AEs leading to withdrawal, dose modification, or treatment discontinuation will be summarized by subgroup and tesevatinib overall according to SOC and preferred terms. All AEs will be in listings. Duration of AEs will be determined and included in listings, along with action taken and outcome.

Laboratory results will be classified according to NCI-CTCAE Version 4.03 and summarized. Laboratory results not corresponding to a coded term will not be graded. Incidence of laboratory abnormalities will be summarized. The worst on-study grade after the first dose of study drug will be summarized. The incidence of  $\geq$  Grade 3 laboratory abnormalities under treatment and shifts in toxicity grading from baseline to highest grade post-baseline will be displayed. Results for variables that are not coded will be presented in the listings as below, within, and above the normal limits of the local laboratory.

Vital sign measurements will be summarized at each scheduled time point using descriptive statistics. Karnofsky performance status results will be summarized by scheduled time point. Additional statistical details will be provided in a prospective statistical plan.

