#### 3.10.1 Adverse Events

AEs will be coded using the MedDRA dictionary (Version 20.1 or higher). Treatment-emergent AEs (TEAEs) are any AE occurring or worsening in severity after the first administration of study medication. All AEs (including SAEs) will be graded using the 5-point Common Terminology Criteria for Adverse Events (CTCAE) V4.03 scale (mild, moderate, severe, life-threatening, or death). Causality with tesevatinib will be classified as: definitely related; probably related; possibly related; unlikely related; or not related.

The investigator will further assess the relationship of AEs to tesevatinib or the underlying disease.

The number and percentage of patients who experienced at least one TEAE as well as the number and percentage of patients who experienced AEs of each specific SOC and PT will be presented. For the presentation of AE incidences, the SOCs and the PTs within each SOC will be presented by decreasing total frequency. Tabulation by maximum severity and relationship to tesevatinib will also be included by treatment group.

The TEAEs, Grade  $\geq$  3 TEAEs, SAEs, and TEAEs leading to dose modification/discontinuation will be summarized by treatment arm, SOC, and PT. These analyses will be repeated for events considered related (definitely related/probably related/possibly related) to tesevatinib.

Subject listings will be provided for SAEs, AEs resulting in study drug discontinuation and deaths.

Adverse events will also be presented in listings. Time to onset and duration of AEs will be included in listings, along with action taken and outcome.

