#### 3.11 Pharmacokinetic and Pharmacodynamic Analysis

PK serum concentration and all biomarkers will be summarized at each collection time-point.

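### The SAP drops the EGFR subgroups from the primary safety objective and safety tables without declaring it, and its biomarker summary does not use the paired tissue.

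*SAP*

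**What the plan says.** **Safety.** Protocol 6.1.2, the primary safety objective, reads "To evaluate the safety and tolerability of tesevatinib in all patients and in the subgroup of patients with EGFRvIII" and goes on to name the EGFR-amplified subgroup as well. Protocol 13.4.6.5 carries this into the analysis: "Safety analyses will present overall results and results by subgroups". It then lists the adverse event outputs that "will be summarized by subgroup and tesevatinib overall according to SOC and preferred terms".

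SAP 2.1.2 gives the objective as "To evaluate the safety and tolerability of tesevatinib in all treated subjects". SAP 3.10.1 says that the main adverse event tables "will be summarized by treatment arm, SOC, and PT". SAP 3.10.2 and 3.10.4 split laboratory and QTcF results by treatment group. No part of SAP 3.10 mentions EGFR status. SAP 3.2 does define Subpopulation A (EGFR-amplified) and Subpopulation B (EGFRvIII-positive), but only the efficacy analyses in 3.8.2 use them.

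**Biomarkers.** Protocol 6.3 asks for a comparison of EGFRvIII expression or other tissue markers "in paired primary and recurrent glioblastoma specimens from the same patient, when these are available", and for the correlation between EGFRvIII positivity and amplification. Protocol 13.4.6.4 leaves the detail of the exploratory analyses to the SAP. The SAP lists no exploratory objectives. Its biomarker plan is one sentence in 3.11, under which "all biomarkers will be summarized at each collection time-point".

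**Declared changes.** SAP 3.1.2 says in general terms that statistical methods in the primary and secondary analyses were changed where needed. It itemises nothing.

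**The concern.** The SAP says in its introduction that it implements Amendment 4 of the protocol, so a reader would expect the objectives to match. They do not. A programmer working from SAP 3.10 would produce overall safety tables and nothing by EGFR status, and the study report would omit part of what the protocol calls its primary safety objective. The arm and group labels add to the problem, because SAP 2.2 describes a single-arm study and the labels refer to nothing.

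For the paired-tissue objective the gap is different. The protocol hands the method to the SAP, and the SAP does not supply one. Summarising each marker separately at each collection point discards the link between two specimens from the same patient, and that link is what the objective is about.

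**Working it through.** No stated power, alpha or sample size is at issue, so there is no plan figure to reproduce. The check is a comparison of text, with some arithmetic for scale.

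**1. Safety, side by side**

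| Item | Protocol | SAP |
|---|---|---|
| Objective | 6.1.2: all patients, EGFRvIII-positive, EGFR-amplified | 2.1.2: all treated subjects |
| Adverse event tables | 13.4.6.5: by subgroup and overall | 3.10.1: by treatment arm or group |
| Laboratory, ECG | 13.4.6.5: under the general rule that safety results are shown overall and by subgroup | 3.10.2, 3.10.4: by treatment group |
| Change declared | – | 3.1.2: not mentioned |

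The SAP's safety population is everyone dosed, so its objective covers the all-patients part of the protocol's. The two subgroup parts have no counterpart in the SAP.

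**2. Paired tissue**

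Protocol 12.1.8 requires samples from the original tumour and any later biopsies, so some patients should have two specimens. A summary at each collection point gives one count for primary specimens and one for recurrent specimens. The same two counts are compatible with every patient keeping their status and with several patients switching in opposite directions. Only a within-patient table separates these cases.

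**3. EGFRvIII by amplification**

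SAP 3.11 does not ask for this cross-table. SAP 3.8.2.1 plans PFS-6 in A, in B and in the two combined, and SAP 3.1.4.2 makes the denominator the number of subjects in the analysed population. (Section 3.8.2.1 cites a section 3.1.3.2 that the SAP does not contain; I read it as 3.1.4.2.) If the combined set is the union, the overlap is n(A) + n(B) − n(union). If it is the intersection, its denominator is the overlap. The counts can therefore largely be recovered, although no table presents them.

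**4. Scale**

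Inputs: N = 40 (protocol 7.1) and assumed shares of 57% amplified and 27% EGFRvIII-positive (protocol Table 7).

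- Amplified: 40 × 0.57 = 22.8, about 23.
- EGFRvIII-positive: 40 × 0.27 = 10.8, about 11.

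Chance of seeing at least one case of an event with a true rate of 10% (an illustrative rate), 1 − 0.9^n:

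- n = 40: 0.985
- n = 23: 0.911
- n = 11: 0.686

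Exact (Clopper-Pearson) 95% intervals for an observed rate near 20%, again illustrative:

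- 8/40: 9.1% to 35.6%
- 5/23: 7.5% to 43.7%
- 2/11: 2.3% to 51.8%

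**The case against.** The strongest reply is that little is lost. Protocol 13.4.6.5 still requires safety by subgroup, and SAP 3.1.2 claims changes only to primary and secondary analysis methods, so it does not withdraw that requirement. SAP section 4 places the table list in a separate document that is not available here and may contain the subgroup tables. The synopsis lists safety objectives without calling them primary. The biomarker items are exploratory, and the paired comparison depends on specimens being available.

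Much of this stands, and it limits what may be concluded. A reader might infer four stronger things that the documents do not support:

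- *That subgroup safety tables produced later would be post hoc.* They would not be. The protocol specifies them, and producing them carries it out.
- *That subgroup safety cannot be answered.* The tables are not called for in the SAP. That is an unreconciled conflict between the two documents, and it does not show that the tables will be missing.
- *That no planned output reveals how far the two EGFR subgroups overlap.* The denominators in SAP 3.8.2.1 largely reveal it where both markers are known.
- *That SAP 3.11 covers only on-treatment visits.* It does not say so. A tissue collection point may be primary or recurrent surgery. What is missing is the pairing within patients.

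Nor does protocol 6.1.2 ask for a comparison of safety between marker-positive and marker-negative patients. It asks for safety in the positive subgroups.

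What the reply does not remove is that SAP 2.1.2 and 3.10 depart from protocol 6.1.2 and 13.4.6.5 without saying so, and that neither document gives a method for the paired tissue.

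**Conclusion.** The point holds in two parts. First, SAP 2.1.2 and 3.10 conflict with protocol 6.1.2 and 13.4.6.5, and SAP 3.1.2 does not declare the change. Followed as written, the SAP leaves the two subgroup parts of the primary safety objective unreported. Second, SAP 3.11 does not use the within-patient pairing that the primary/recurrent tissue objective calls for.

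The size is modest. With about 23 and 11 of 40 patients, subgroup safety tables are descriptive and no design figure changes. Those counts rest on the Table 7 shares and full enrolment; patients with unknown marker status would reduce them. The conclusion also assumes that the separate table list does not already supply the missing outputs. If it does, the SAP text still needs correcting. This should be put right, but it does not threaten the primary efficacy analysis.

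**What to change.** - **SAP 2.1.2:** restore the protocol's objective, with both subgroups.
- **SAP 3.10:** replace the arm and group labels with columns for all patients, Subpopulation A and Subpopulation B. Columns for non-positive and unknown status are optional. Apply them to all AEs and SAEs and their treatment-related subsets; to AEs of Grade 3 or above and their related subset; to AEs that led to withdrawal, a change of dose or discontinuation; and to laboratory and ECG results. Label the subgroup columns descriptive.
- **SAP 3.11:** add a plain cross-table of EGFRvIII by amplification with counts, including unknown. Add a within-patient cross-table of primary against recurrent status where both specimens exist, or the paired change for a continuous marker.
- **SAP 3.1.2:** name any of these items that the sponsor intends to drop, with the reason.

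Plain counts are enough. An agreement coefficient would mislead for two different markers. If all 11 EGFRvIII-positive patients were among the 23 amplified, agreement would be (11 + 17)/40 = 0.70, expected agreement (23 × 11 + 17 × 29)/1600 = 0.466, and kappa (0.70 − 0.466)/(1 − 0.466) = 0.44, although the overlap is the largest possible.

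Protocol 13.4.6.4 words the marker correlation as being with respect to survival and safety. The cross-table alone does not address that. Read with the new safety columns and the OS analyses in A and B already planned in SAP 3.8.2.4, it gives a descriptive account.

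The cost is SAP wording, a few extra columns and two small tables, all from data that the protocol already collects. The downside is more output with wide intervals, which readers must be told not to over-interpret.

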#### 2.1.3 Secondary Objectives

The secondary objectives of this study are:

- To evaluate the efficacy of tesevatinib as measured by investigator-assessed progression-free survival rate at 6 months (PFS-6) in Subpopulations A and B.
- To evaluate the efficacy of tesevatinib as measured by the OS-9 rate, in all patients and in those in Subpopulations A and B
- To evaluate the efficacy of tesevatinib as measured by the PFS, in all patients and in those in Subpopulations A and B
- To evaluate the efficacy of tesevatinib as measured by the OS, in all patients and in those in Subpopulations A and B
- To evaluate the efficacy of tesevatinib as measured by ORR and DOR per RANO criteria, and DOR in all patients and in Subpopulations A and B
- To evaluate the efficacy of tesevatinib as measured by PFS-6, OS-9, ORR and DOR in:
  - $\circ \quad EGFRvIII^{pos} \ vs \ EGFRvIII^{neg}$
  - EGFR amplificationpos vs EGFR amplificationneg

## 2.2 Study Design

This is an open-label, single dose arm, multicenter, Phase 2 study to assess the activity of tesevatinib in patients (n = 40) with recurrent glioblastoma. This study will be conducted at up to 10 sites in the United States.

Subjects meeting inclusion/exclusion criteria receive tesevatinib at the dose of 300 mg once daily. One cycle will be defined as 28 days of treatment. Subjects will be treated with study drug until disease progression or unacceptable toxicity occurs.

All patients also will be followed for a period of 30 days following their last dose of tesevatinib or until the patient starts a new treatment.

## 2.3 Visit Schedule and Study Assessment

The flow chart of visit schedule and study assessments is given in Table 1 of the KD019-208 Protocol.

# **3** STATISTICAL METHODS

## 3.1 General Methods

#### 3.1.1 Computing Environment

All statistical programming and data analyses will be performed using SAS® Version 9.4 on Windows platform.

## 3.1.2 Changes from protocol

Changes from protocol in statistical methods are made in both primary and secondary analyses wherever necessary.

#### 3.1.3 Sample Size Justification and power calculations:

The power calculation is based on simulations in the Weibull distribution to describe the progression and survival times. The estimation of PFS-6 is done using the Cox model. Based on a one-stage design, with a sample size of 40 patients in the overall population, a PFS-6 of 25% and median PFS of 4.5 months, the trial has 95% power to demonstrate an estimated PFS-6 >15%. Based on a one-sided test on a 5% significance level, the trial has 95% power to show a significant difference above the null hypothesis of 7% and 80% power to show a significant difference above 10%. The study is not powered to detect differences in the secondary endpoints.

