# **13.2.** Sample Size Justification

This phase 2 trial is designed primarily to allow a preliminary assessment of the efficacy and safety of tesevatinib in the overall population of 40 patients with recurrent glioblastoma as well as to permit exploratory comparisons between predefined subgroups (by EGFRvIII mutation status and by EGFR gene amplification status). The target PFS-6 rate in the overall study population is 25%. PFS-6 rates seen in randomized studies with bevacizumab [Weathers 2015; Taal 2014; Galanis 2015] are of the order of 15-18%. Bevacizumab is registered in this indication.

With a sample size of 40 patients in the overall population, PFS-6 = 25% and median PFS-6 = 4.5 months, the trial has 95% power of having an estimated PFS-6 > 15%. Addressing uncertainty by the lower 90% confidence limit of the estimated PFS-6 – corresponding to a one-sided test on 5% significance level, the trial has 95% power to show a significant difference above 7% and 80% power to show a significant difference above 10%.

The power calculation is based on simulations in the Weibull distribution to describe the progression and survival times. The median PFS and the PFS-6 and the corresponding shape and scale parameters from the Weibull distribution are shown in Table 6 below.

	Median PFS (months)	6 month PFS	Weibull shape parameter	Weibull scale parameter
Overall population	4.5	25%	5.24	2.41

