#### 3.1.4.2 Binary Endpoint and Other Categorical Variables

For endpoints with two possible outcomes such as alive/otherwise or response/otherwise within specific periods, the 95% confidence interval will be calculated with Clopper-Pearson method for survival rates or response rates. For

other categorical variables, the counts and percent of each category within a parameter will be calculated for observed data only. The denominator for all percentages, unless otherwise specified, will be the number of subjects in the cohort or in the specified analysis population.

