## **3.8 Primary Endpoint Analysis**

## 3.8.1 Progression-Free Survival Rate at 6 Month (PFS-6)

Proportion of patients who are alive and not progressed at 6 months (24 weeks) will be analyzed with method as described in3.1.4.2. This analysis is based on mITT population. Patients whose survival or response status at 6 months (24 weeks) are unknown are not considered alive or progression free. Response Assessment in Neuro-Oncology (RANO) criteria are used to determine specific criteria for treatment response (Appendix 2 of the protocol.) in all endpoint analysis in this study.

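### SAP 3.1.3 states power for the protocol's Cox analysis, but the SAP's primary analysis is a binomial proportion with a 95% interval only; if 25% is the 24-week rate, the two 95% figures become 90.4%

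*SAP*

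**What the plan says.** SAP 3.1.3 carries over the power paragraph of the protocol synopsis. It assumes 40 patients, a PFS-6 of 25% and a median PFS of 4.5 months, and states that "The estimation of PFS-6 is done using the Cox model". It gives 95% power for an estimated PFS-6 above 15%. Then, "Based on a one-sided test on a 5% significance level", it gives "95% power to show a significant difference above the null hypothesis of 7% and 80% power to show a significant difference above 10" per cent.

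Protocol 13.2 ties that test to an interval: "Addressing uncertainty by the lower 90% confidence limit of the estimated PFS-6". Protocol 13.4.6.1 accordingly plans both 95% and 90% two-sided intervals, from a Cox model with a Karnofsky covariate and a gamma frailty for centre.

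The SAP's own primary analysis is in 3.8.1: "Proportion of patients who are alive and not progressed at 6 months (24 weeks) will be analyzed with method as described" in 3.1.4.2, where "the 95% confidence interval will be calculated with Clopper-Pearson method for survival rates or response rates". Section 3.8.1 adds: "Patients whose survival or response status at 6 months (24 weeks) are unknown are not considered alive or progression free". Outside 3.1.3 the SAP mentions no 90% interval and no one-sided test of PFS-6. On departures from the protocol, SAP 3.1.2 says only: "Changes from protocol in statistical methods are made in both primary and secondary analyses wherever necessary".

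**The concern.** The power in SAP 3.1.3 belongs to an estimator that the SAP no longer uses for the primary endpoint. A binomial count of 40 is coarse, so moving one outcome across a threshold shifts power by several points. Counting unknown status as failure also lowers the rate being tested.

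The error level is mismatched too. A one-sided 5% test corresponds to the lower limit of a two-sided 90% interval, and the SAP plans only a 95% interval. A reader using that interval would in effect be testing at one-sided 2.5%, and SAP 3.8.1 gives no decision rule to prevent this. The same trial result could then be called significant or not against 10%, depending on which part of the SAP is followed.

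**Working it through.** **Inputs.** n = 40; PFS-6 25%; median PFS 4.5 months; benchmarks 15%, 7% and 10%; one-sided 5% (SAP 3.1.3, Protocol 13.2). Weibull parameters 5.24 and 2.41 (Protocol Table 6). Assessment at 24 weeks, unknown = failure (SAP 3.8.1). 95% Clopper-Pearson interval (SAP 3.1.4.2).

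**1. The stated figures under a Cox-type estimate.** S(4.5) = 0.50 and S(6) = 0.25 give shape = ln 2 / ln(6/4.5) = 2.41 and scale = 6 / (ln 4)^(1/2.41) = 5.24. These are Table 6's values with the two column labels exchanged.

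With no covariate, frailty or censoring before 6 months, and X patients event-free, the Breslow estimate is exp(−H), where H is the sum of 1/i for i = X+1 to 40. Using the log-log lower limit of a 90% interval:

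| X | Breslow estimate | Lower 90% limit |
|---|---|---|
| 6 | 16.1% | 8.0% |
| 7 | 18.5% | 9.8% |
| 8 | 21.0% | 11.6% |

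So 6/40 is enough for an estimate above 15% and for 7%, and 8/40 is needed for 10%. Under Binomial(40, 0.25), P(X ≥ 6) = 95.7% and P(X ≥ 8) = 81.8%. The stated 95/95/80 is therefore attainable for a Cox estimate. This omits the Karnofsky covariate and the frailty, so it is not a full check of the protocol's model.

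**2. The SAP's analysis, 25% at 24 weeks, complete data.**

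| X/40 | Proportion | Exact one-sided p vs 7% | p vs 10% | Lower limit, 90% interval | Lower limit, 95% interval | P(≥ X) at 25% |
|---|---|---|---|---|---|---|
| 6 | 15.0% | 0.058 | 0.206 | 6.7% | 5.7% | 95.7% |
| 7 | 17.5% | 0.020 | 0.0995 | 8.5% | 7.3% | 90.4% |
| 8 | 20.0% | 0.006 | 0.042 | 10.4% | 9.1% | 81.8% |
| 9 | 22.5% | 0.002 | 0.015 | 12.3% | 10.8% | 70.0% |

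- Estimate above 15%: 6/40 is exactly 15%, so 7/40 is needed. Probability 90.4% (stated 95%).
- Against 7%: 7/40 is needed with either interval. Power 90.4% (stated 95%).
- Against 10%: 8/40 at one-sided 5%, power 81.8% (stated 80%); 9/40 by the 95% interval, power 70.0%.

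The drop from 95.7% to 90.4% is the single outcome 6/40, with P(X = 6) = 5.3%.

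**3. If the 25% is the rate at 6 calendar months.** 24 weeks = 168/30.44 = 5.52 months, and S(5.52) = exp(−(5.52/5.24)^2.41) = 32.2%. Binomial(40, 0.322) gives P(X ≥ 7) = 98.8%, P(X ≥ 8) = 97.0% and P(X ≥ 9) = 93.5%.

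**4. Unknown status as failure.** The documents give no rate, so a fraction u of 5% to 20% is assumed and the rate is multiplied by (1 − u).

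| Reading of the 25% | Rate, u = 5% to 20% | Above 15%, and vs 7% | vs 10% (90% interval) |
|---|---|---|---|
| 24 weeks | 23.75% to 20.0% | 87.0% to 71.4% | 76.7% to 56.3% |
| 6 calendar months | 30.6% to 25.8% | 98.0% to 92.0% | 95.3% to 84.5% |

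**The case against.** The strongest reply is that Table 6 puts the 25% under a 6-month heading beside a median in months, and its Weibull parameters fit only that pair on one month scale. Read in calendar months, the SAP's analysis has more power than stated, not less. That stands as a limit on the direction of the error. It does not settle the reading, because both documents define PFS-6 as 6 months (24 weeks), and it does not make 3.1.3 a description of the planned analysis.

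It can also be said that the stated figures are not miscalculated, since they are reproducible for the method 3.1.3 names. That is right: the fault lies in carrying them over to another method. The gap also depends on the interval scale, because a plain 90% limit around the Breslow estimate at 6/40 is 6.6%, so a Cox-type analysis on that scale would also give 90.4% against 7%. The documents do not say which scale was used.

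Two further points are fair. The 80% figure survives at the stated one-sided 5%, and 70.0% arises only if the 95% interval is used as the rule, which the SAP does not say. The 5% to 20% range for unknown status is an assumption, and censoring would cost a Cox analysis precision as well.

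Finally, this is a preliminary single-arm trial, n = 40 is unaffected, and a 90% limit can be derived from the reported count. That limits the seriousness. It does not justify a SAP whose power statement, error level and primary method disagree.

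**Conclusion.** The concern holds. SAP 3.1.3 gives the power of an analysis that the SAP has replaced. With 40 patients and complete data, power against 7% for the planned analysis is 90.4% if the 25% applies at 24 weeks and 98.8% if it applies at 6 calendar months; the stated figure is 95%. Against 10% at one-sided 5% it is 81.8% or 97.0%; the stated figure is 80%. All four fall if any patient's status is unknown.

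The interval mismatch holds under either reading. A result of 8/40 is significant against 10% at the stated level (p = 0.042; 90% lower limit 10.4%), yet the only planned interval has a lower limit of 9.1%. Confidence is high on the mismatch. Whether the stated power is too high or too low cannot be settled from the documents. The trial's validity is not in question, but the SAP should be corrected.

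**What to change.** Change the SAP only.

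1. **Section 3.1.3.** Keep the existing figures, labelled as the protocol's Weibull/Cox justification for n = 40. State whether the 25% refers to the 24-week assessment or to 6 calendar months. Then add the matching sentence. For 24 weeks: *For the exact binomial analysis in 3.8.1 with 40 patients, complete data and a 25% rate at the 24-week assessment, the probability of an observed PFS-6 above 15% is 90%, and power at one-sided 5% is 90% against 7% (at least 7/40) and 82% against 10% (at least 8/40). Unknown status counted as failure lowers these figures.* For 6 calendar months, the rate at 24 weeks is 32.2% and the three figures are 99%, 99% and 97%.
2. **Section 3.8.1.** Restore the two-sided 90% interval (Clopper-Pearson) and identify it as the one matching the one-sided 5% test. Keep the 95% interval for reporting.
3. **Section 3.1.2.** Name the change from the Cox gamma frailty model to a binomial proportion with unknown status counted as failure.

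The cost is three wording changes and one extra interval in the output. It needs no extra patients or data and no change to the protocol's figures.
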